8.2. Efficacy Assessments

8.2.1. Celiac Disease Patient-Reported Outcome (CeD PRO)

Subjects will assess their symptoms daily in the CeD PRO using the eDiary throughout the study. This questionnaire was specifically developed and validated to assess symptom severity in clinical trials of celiac disease (Leffler 2015) and is accepted by Health Authorities as a registration endpoint for marketing authorization. The symptom domains within the CeD PRO are illustrated in Figure 2.

Items in the questionnaire were formulated based on one-on-one interviews with patients with celiac disease, thus they reflect the symptoms that patients consider part of their celiac disease experience. The questionnaire is designed as a self-administered daily diary to be completed at the same time each day and requires less than 10 minutes to complete. It includes 9 items asking participants about the severity of celiac disease symptoms they may experience each day.

[figure not shown]
Participants are asked to rate their symptom severity on an 11-point (0 to 10) scale; from “not experiencing the symptom” to “the worst possible symptom experience”. Symptoms include abdominal cramping, abdominal pain, bloating, gas, diarrhea, loose stool, nausea, headache, and tiredness.

The Abdominal Symptoms domain refers to questions regarding abdominal pain, abdominal cramping, bloating, or gas in the CeD PRO questionnaire.

Analyses will be performed on all individual domain scores and weekly worst symptom domain scores in the GI domains (Abdominal Symptoms and Diarrhea/Loose Stool domains) and Total GI score (Abdominal Symptoms Domain + Diarrhea/Loose Stool Domain + Nausea item). The Total GI score will be assessed with and without inclusion of the Nausea item.

The copyright of the CeD PRO [2015] is held by 9 Meters Biopharma and was formerly held by Alba Therapeutics Corporation. The CeD PRO is used with permission.

Figure 2 Symptom Domains in the Celiac Disease Patient-Reported Outcome Questionnaire

See Appendix 10.4 for the instrument.

8.2.2. Stool Frequency Question Based on BSFS

The BSFS is a pictorial aid to help subjects identify the shape and consistency of their stools during the study (Riegler 2001). The subject will be asked to record the number of stools that have a consistency of Type 6 or 7 (loose stool or entirely liquid) at bedtime daily in the eDiary. On the days in which the subject experiences no such stool (BSFS Type 6 or 7), the subject should record 0 in the eDiary instead of leaving it blank.

See Appendix 10.4 for the instrument.

8.2.3. Gastrointestinal Symptom Rating Scale (GSRS)

The GSRS is a 15-question, 7-point-scale questionnaire used to assess 5 dimensions of GI syndromes: diarrhea, indigestion, constipation, abdominal pain, and reflux (Svedlund 1988). The recall period is 1 week before the assessment. While not specific for celiac disease, the GSRS is widely used in gastroenterology and has been used in several clinical trials of experimental medications in celiac disease (Kelly 2013; Lähdeaho 2011; Leffler 2015).

See Appendix 10.4 for the instrument.

8.2.4. Investigator Global Assessment of Disease

The IGA is a 5-point Likert scale designed for use by the Investigator or qualified sub-investigator to assess the subject's clinical disease activity at each specified time point. The same assessor should be used at each specified time point if possible.

See Appendix 10.4 for the instrument.

8.2.5. PROACTIVE Dietary Questionnaire

The PROACTIVE Dietary Questionnaire (See Appendix 10.4) is a two-question instrument to assess potential inadvertent exposure to gluten. The questionnaire will be completed on a weekly basis (every Monday) to assess dietary habits during the previous week.

8.2.6. Patient Global Impression of Severity and Change

In the current study, data collected from the PGIS and PGIC instruments will assist in future analyses of clinically meaningful change for the Abdominal Symptoms domain of the CeD PRO.

8.2.6.1. Patient Global Impression of Severity (PGIS)

Subjects will be asked to complete the PGIS every 2 weeks in the eDiary, from the evening of eDiary dispensation at Visit 1 (Day -28) through the end of the study.

Subjects will be asked to assess the severity of their symptoms as follows:

“Please choose the response that best describes the severity of your celiac disease over the past 7 days (check one response): None, Mild, Moderate, Severe, Very Severe.”

8.2.6.2. Patient Global Impression of Change (PGIC)

Subjects will be asked to complete the PGIC every 2 weeks in the eDiary, beginning 2 weeks after the first dose of study drug administration at Visit 1.

Subjects will be asked to compare their symptoms to those before treatment as follows:

“Please choose the response below that best describes the overall change in your celiac disease symptoms since you started taking the study medication: Much better, A little better, No change, A little worse, Much worse.”

8.2.7. Esophagogastroduodenoscopy (EGD) and Histological Assessments

At each time point specified in the SoA (Section 1.3), at a minimum, 6 biopsies or specimens of small-bowel tissue will be taken from the second part of the duodenum distal to the ampulla (duodenum D2) by EGD and endoscopic forceps biopsy. Ulcerative lesions should be avoided for all biopsies. The biopsies should be opaque and not translucent or stringy. Poor specimens should be replaced. The location and macroscopic appearance of the tissue will be noted in the source documents. The potential presence of any observable lesion such as ulcerative jejunitis will also be captured. When necessary, samples will be re-oriented and sectioned again until they are of good quality. The procedures will be described in a Study or Laboratory Manual or a similar document. The biopsies or specimens will be prioritized as follows:

1. All 6 specimens will be fixed in PAXgene at the site (see Central Laboratory Manual) and shipped to the Central Pathologist.
2. The Central Pathologist, blinded to treatment assignment, will assess villus height (VH, in micrometers) and crypt depth (CD, in micrometers) and their ratio, VH:CD, using 4 specimens. Further, the Marsh-Oberhuber histology score will be given (M0, M1, M2, M3a, M3b, or M3c) and the density of CD3-positive IELs (cells/100 epithelial cells) will be assessed. Histology analysis will be performed following standard operating procedures for fixed biopsy specimen orientation, paraffin embedding, cutting, staining, and scanning for whole slide virtual microscopy. Standard operating procedures will also be followed for biopsy morphometry readings using validated methods (Taavela 2013). If it is not feasible to measure at least 3 villus-crypt units for a subject's given biopsies, even after re-cutting, the results will be considered not evaluable.
3. Two specimens will be placed in a messenger ribonucleic acid (mRNA) preservative for future mRNA analysis of inflammatory pathways (e.g., expression analysis of IL-15-related pathways to potentially identify predictive biomarkers of response to PRV-015).

Every effort will be made to collect at least all 6 specimens, but if this number cannot be reached, the specimens will be allocated in the order indicated above. Sites may collect a maximum of 2 additional duodenal biopsy fragments for local clinical and/or research purposes. Additional biopsies of unexpected abnormalities or diseases that are excluded from the study may also be taken and processed locally.

8.2.8. Celiac Disease-Related Serology

Anti-tTG auto-antibodies, while not very responsive to modest dietary transgressions, constitute a specific tool to assess disease activity in response to large amounts of gluten over a period of time of at least 8-12 weeks (Lähdeaho 2011; Kelly 2013). Blood samples will be collected at the specified visits to determine the levels of serum anti-tTG antibodies (see Section 1.3). Anti-tTG IgA and IgG are analyzed in blood at screening and in serum thereafter using enzyme-linked immunosorbent assay (ELISA).

Anti-DGP antibodies are more responsive than anti-tTG to gluten consumption and have been detected in some celiac patients who are negative for anti-tTG due to the different kinetics between the antibodies and the possibility of IgA deficiency and a false negative anti-tTG IgA. Thus, anti-DGP IgG is a sensitive antibody to measure celiac disease activity (Brusca 2015). Blood samples will be collected to analyze serum anti-DGP antibodies (IgA) by ELISA at specified visits (see Section 1.3).

8.2.9. Gluten Stool and Urine Tests

The G12 antibody-based stool and urine gluten tests are validated assays used to assess patient compliance with gluten challenge and to measure possible gluten contamination in research studies. The assay detects and quantifies gluten consumption by measuring gluten immunogenic peptides in stool (Comino 2012) and urine (Moreno 2015).

Subjects are instructed to collect a stool sample approximately every 2 weeks, before each scheduled visit and bring it to the site or provide the sample during the visit if possible. If this is not possible, a stool sample collected within 3 days before and 3 days after a visit is acceptable.

For at-home visits, samples are not collected. Urine sample for gluten testing will be collected during the office visit.

8.3. Safety Assessments

Planned timepoints for all safety assessments are provided in the SoA.

8.3.1. Physical Examinations

A complete physical examination, required at screening, Visit 1, Visit 15, and Visit 16, will include, at a minimum, assessments of the head, eyes, ears, nose and throat, cardiovascular, respiratory, gastrointestinal and neurologic systems and skin, extremities, and lymph nodes. A brief physical examination at other specified visits (Section 1.3) will include, at a minimum, assessments of the skin, lungs, cardiovascular system, abdomen (liver and spleen), and areas of previously noted abnormalities.

Height will be measured and recorded at screening. Weight will be measured at all physical examinations.

8.3.2. Vital Signs

Vital signs include BP, respiratory rate, heart rate, and body temperature (axillary or oral).

Measurements of BP and heart rate will be assessed supine or sitting, after the subject has rested for at least 5 minutes in a quiet setting without distractions.

The investigator will note if vital signs are normal or abnormal and, if abnormal, whether they are clinically significant or not.

Cut-off values considered to be potentially clinically important (PCI) will be outlined in the Statistical Analysis Plan (SAP).

8.3.3. Electrocardiograms

Single 12-lead ECG will be obtained at screening for study eligibility. The Investigator should note whether it is normal, abnormal not clinically significant, or abnormal clinically significant.

8.3.4. Clinical Safety Laboratory Assessments

Clinical safety laboratory tests are among the overall laboratory tests listed in Section 8.1.

The Investigator must review the laboratory report, document this review, and determine whether any clinically relevant changes occurring during the study should be classified as an AE or not.

Cut-off values for PCI laboratory abnormalities will be outlined in the SAP and Laboratory Manual.

8.4. Adverse Events and Serious Adverse Events

All AEs will be reported by the subject.

The Investigator and any qualified designees are responsible for detecting, documenting, and recording events that meet the definitions of an AE or SAE (see Section 10.2) and remain

responsible for following up AEs that are serious, considered related to the study drug or study procedures, or that caused the subject to discontinue the study drug (see Section 7).

8.4.1. Time Period and Frequency for Collecting AE and SAE Information

All AEs and SAEs will be collected from the signing of the ICF through the final visit (Visit 16) as specified in the SoA (Section 1.3).

TEAEs will be collected from the first post-randomization dose of the study drug administration at Visit 3 through the final visit (Visit 16) as specified in the SoA (Section 1.3). The AEs and SAEs reported during the screening and single-blind placebo run-in periods will be reported separately from the TEAEs.

All SAEs will be recorded and reported to the sponsor or designee immediately upon observing or learning of the event and under no circumstance should this exceed 24 hours, as indicated in Appendix 10.2. Information about the SAE should be as complete as possible and include causality. The Investigator will submit any updated SAE data to the sponsor within 24 hours of it being available.

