10.2.1. Definition of AE

AE Definition

• An AE is any untoward medical occurrence in a patient or clinical study subject, temporally associated with the use of study drug, whether or not considered related to the study drug.• NOTE: An AE can therefore be any unfavorable and unintended sign (including a clinically significant abnormal laboratory finding), symptom, or disease (new or exacerbated) temporally associated with the use of study drug.• A treatment-emergent AE (TEAE) is defined as an AE that occurs from the first dose of post-randomization study drug administration through the end of the study.

Events Meeting the AE Definition

• Any abnormal laboratory test results (hematology, clinical chemistry, or urinalysis) or other safety assessments (e.g., ECG, radiological scans, vital signs measurements), including those that worsen from baseline, considered clinically significant in the medical and scientific judgment of the Investigator (i.e., not related to progression of underlying disease).• Exacerbation of a chronic or intermittent pre-existing condition including either an increase in frequency and/or intensity of the condition.• New conditions detected or diagnosed after study drug administration even though it may have been present before the start of the study.• Signs, symptoms, or the clinical sequelae of a suspected drug-drug interaction.• Signs, symptoms, or the clinical sequelae of a suspected overdose of either study drug or a concomitant medication. Overdose per se will not be reported as an AE/SAE unless it is an intentional overdose taken with possible suicidal/self-harming intent. Such overdoses should be reported regardless of sequelae.• The signs, symptoms, and/or clinical sequelae resulting from lack of efficacy will be reported as AE or SAE if they fulfil the definition of an AE or SAE. Also, “lack of efficacy” or “failure of expected pharmacological action” also constitutes an AE or SAE.

Events NOT Meeting the AE Definition

- Any clinically significant abnormal laboratory findings or other abnormal safety assessments which are associated with the underlying disease, unless judged by the Investigator to be more severe than expected for the subject's condition.
- The disease/disorder being studied or expected progression, signs, or symptoms of the disease/disorder being studied, unless more severe than expected for the subject's condition.

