- The Investigator will also consult the Investigator’s Brochure (IB) and/or Product Information, for marketed products, in his/her assessment.
- For each AE/SAE, the Investigator **must** document in the medical notes that he/she has reviewed the AE/SAE and has provided an assessment of causality.
- There may be situations in which an SAE has occurred and the Investigator has minimal information to include in the initial report to the CRO. However, it is very important that the Investigator always make an assessment of causality for every event before the initial transmission of the SAE data to the CRO.
- The Investigator may change his/her opinion of causality in light of follow-up information and send a SAE follow-up report with the updated causality assessment.
- The causality assessment is one of the criteria used when determining regulatory reporting requirements.

Follow-up of AEs and SAEs

- The Investigator is obligated to perform or arrange for the conduct of supplemental measurements and/or evaluations as medically indicated to elucidate the nature and/or causality of the AE or SAE as fully as possible. This may include additional laboratory tests or investigations, histopathological examinations, or consultation with other health care professionals.
- If a subject dies during participation in the study or within 3 months of the last dose, the Investigator will provide the Sponsor with a copy of the death certificate, hospitalization records and any post-mortem findings including histopathology where available
- New or updated information will be recorded in the originally completed CRF.
- The Investigator will submit any updated SAE data to the CRO within 24 hours of receipt of the information.

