8.7.2 Adverse Events

Adverse Events (AEs) and serious adverse events (SAEs) are collected from the signing of the ICF until final visit (Visit 16) and will be classified by System Organ Classes (SOC) and Preferred Terms (PT) using the latest MedDRA dictionary applicable at the time of database lock.

Treatment-emergent adverse events (TEAEs) are collected from the first dose of double-blind study drug until the last dose of double-blind study drug + 42 days. The AEs and SAEs reported during the screening period (those which started after the first screening visit and ended before the start of run-in period or ongoing at the time of run-in period) and single-blind placebo run-in period AEs and SAEs (those which started after visit 1 (first run-in period visit) and ended before the start of double-blind randomized treatment period or ongoing) will be reported separately from the TEAEs.

AEs reported during post-treatment period, i.e. starting at the end of treatment emergent period will be summarized by System Organ Classes (SOC) and Preferred Terms (PT).

Injection site reactions are those identified programmatically using the MedDRA High Level Term of "Injection site reactions".

Adverse Events of Special Interest (AESI) are (1) severe opportunistic infections and (2) hypersensitivity reactions of at least moderate severity. AESI will be programmatically identified for summarization based on the criteria below using MedDRA Preferred Term or Standardized MedDRA Queries (SMQ) (narrow) which also meet severity/seriousness criteria in the eCRF:

Table 3 AESI Criteria

AESI Category	eCRF AE page	MedDRA Search Terms
Severe opportunistic infections	"Severe" or Serious noted in eCRF	PT included in SMQ (narrow) of Opportunistic infections (SMQ) (20000235)
Hypersensitivity reactions of at least moderate severity	"Moderate", "Severe", or Serious noted in eCRF	PT contains "Hypersensitivity" or "hypersensitivity" OR PT included in SMQ (narrow) of • Anaphylactic reaction (SMQ) (20000021) • Hypersensitivity (SMQ) (20000214) • Severe cutaneous adverse reactions (SMQ) (20000020) • Drug reaction with eosinophilia and systemic symptoms syndrome (SMQ) (20000225) • Angioedema (SMQ) (20000024)

An overall summary table of treatment-emergent adverse events will be produced and will present the number and proportion (%) of subjects in each treatment group who have at least one adverse event in the following categories:

- TEAE

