- TEAE related to study drug (possible, probable, or definite attribution)
- TEAE severity (mild, moderate, severe)
- TEAE leading to study treatment discontinuation
- TEAE leading to death
- · Treatment-emergent injection site reactions
- Treatment-emergent SAE
- Treatment-emergent AESI

In case of more than one reported severity (e.g., mild, moderate, severe) and/or causality (e.g., unrelated, unlikely, possible, probable, definite) the worst outcome is used for reporting, respectively.

Summary tables presenting the number and proportion (%) of subjects in each treatment group who have at least one adverse event in the following categories will be presented by SOC and PT:

- TEAE
- AEs occurring during the Screening period (All Screened analysis set)
- AEs occurring during the Run-in period (Run-in analysis set)
- TEAE related to study drug (possible, probable, or definite attribution)
- Severe TEAE
- TEAE leading to study treatment discontinuation
- TEAE leading to death

- Treatment-emergent injection site reactions
- Treatment-emergent SAE
- SAE occurring during the Screening period (All Screened analysis set)
- SAE occurring during the Run-in period (Run-in analysis set)
- Treatment-emergent AESI

For the summaries of severe TEAE, serious TEAE, treatment-emergent AESI, and TEAE leading to study treatment discontinuation, the risk differences (comparing PRV-015 arms to placebo) and exact 95% CI (using the Clopper-Pearson method) will be provided for each SOC or PT.

A summary table presenting the number and proportion (%) of subjects in each treatment group who have at least one TEAE will be presented by descending frequency of PT.

For summary tables by SOC/PT or by PT, subjects will be counted once in the applicable row.

Data listings will also be provided for AEs and SAEs occurring during Screening and Run-in periods, respectively. Additional data listings of TEAEs will be provided.

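### Neither document says whether an AE recorded before the first double-blind dose becomes treatment-emergent if it worsens or turns serious afterwards, and the SAP's start-date rule leaves it out by default

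*Protocol*

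**What the plan says.** Protocol 10.2.1 says that a TEAE "is defined as an AE that occurs from the first dose of post-randomization study drug administration through the end of the study". Protocol 8.4.1 uses the same starting point and adds: "The AEs and SAEs reported during the screening and single-blind placebo run-in periods will be reported separately from the TEAEs".

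SAP 8.7.2 says that TEAEs "are collected from the first dose of double-blind study drug until the last dose of double-blind study drug + 42 days". It then describes the events to be reported apart from them. The run-in group consists of events "those which started after visit 1 (first run-in period visit) and ended before the start of double-blind randomized treatment period or ongoing". The screening group is built the same way and also includes events still ongoing when run-in begins. Under Protocol 9.4, the final analyses follow the SAP.

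Two passages in Protocol Appendix 2 bear on how a worsening reaches the database. Section 10.2.1 lists exacerbation of a pre-existing condition, in frequency or intensity, among the events that are AEs. Section 10.2.3, on follow-up, says: "New or updated information will be recorded in the originally completed CRF".

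Footnote 17 of the Schedule of Activities (Protocol 1.3, repeated in SAP 11.1) restricts recording before the first post-randomization dose to SAEs and AEs related to study procedures. Protocol 8.4.1 says that all AEs and SAEs are collected from consent, with a reference to the Schedule of Activities.

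**The concern.** TEAEs, TEAEs leading to treatment discontinuation, treatment-emergent SAEs and AESIs are named safety endpoints (Protocol 3, SAP 3.2). SAP 8.7.2 gives risk differences against placebo with exact 95% intervals for severe TEAEs, serious TEAEs, AESIs and TEAEs leading to discontinuation. A TEAE definition that looks only at when an event began cannot see harm that consists of making an existing event worse.

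Pre-dose events arise before randomization, so their frequency should be balanced across arms on average. What randomization does not balance is worsening caused by the drug, and that is what these tables are meant to show. If worsening stays attached to the old start date, any such effect is under-counted in the active arms. If sites differ in how they record it, the same clinical course appears in different tables.

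**Working it through.** No figure in the plan covers this point, so the check is to apply the documents' rules to each type of event.

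1. **Pre-dose AE on the CRF, ongoing at Visit 3, then worsens.** If the original record is updated (Protocol 10.2.3), the start date stays before the first dose. SAP 8.7.2 then keeps it in the screening or run-in group. If the worsening is entered as a new exacerbation AE (Protocol 10.2.1), its start date is post-dose and it is a TEAE. No passage chooses between the two.

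2. **Pre-dose AE becomes serious after Visit 3.** The same two routes exist. With an update, the event is absent from the treatment-emergent SAE table and could enter the run-in SAE table instead.

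3. **Pre-dose AE leads to stopping double-blind drug without worsening.** There is no exacerbation to enter as a new AE, so it is not a TEAE and is absent from the discontinuation table by system organ class and preferred term. The stop itself still appears in disposition by reason (SAP 8.3), and the event appears in the pre-dose tables and listings.

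4. **Non-serious, non-procedural complaint in run-in.** If footnote 17 is followed, there is no CRF record before Visit 3. A later worsening is entered for the first time with a post-dose date and is a TEAE, so nothing is lost. If all AEs are recorded from consent, this becomes case 1.

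5. **Start date completely missing, with the end date missing or after the start of double-blind treatment.** SAP 8.2.3 imputes the start of double-blind treatment, so the event is a TEAE.

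Cases 1 and 5 together show an imbalance. An event of unknown onset is counted as treatment-emergent as a precaution, while one known to have worsened on treatment may not be.

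The gap does not come from different windows. Both documents start at the first double-blind dose. For completers the ends also coincide: Visit 14 is Day 155, 155 + 42 = 197, and Day 197 is Visit 16.

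Weight of one subject: with about 220 / 4 = 55 per arm (Protocol 9.2), one missed subject is 1 / 55 = 1.8% of an arm. The number of such subjects cannot be derived, because the documents give no run-in AE rate and no rate of later worsening.

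**The case against.** The strongest reply is that the protocol already treats worsening as an AE. Section 10.2.1 includes exacerbated disease in its AE definition, and it excludes day-to-day fluctuation of existing conditions only where they do not worsen. The sentence in 10.2.3 closes a list about follow-up investigations and post-mortem findings. It mentions neither start dates nor a ban on a new AE entry, and the CRF completion rules are not among the documents. This stands. A reader might infer that TEAEs are fixed by onset alone and that a worsened run-in event can reach no TEAE table, but the documents do not support that. What they leave is an unresolved choice of route.

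Footnote 17 is the second reply. If it governs, only procedure-related AEs and SAEs can be affected, and of those only the ones that persist past Visit 3 and then worsen. This also stands, and it argues for a small number. It does not remove the gap, because those events are recorded under either rule and because 8.4.1 reads more broadly.

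A reader might also infer that the run-in table will show severity reached on PRV-015, because SAP 8.7.2 says that "the worst outcome is used for reporting" with no cut at the first double-blind dose. The documents do not support that either. The planned run-in AE and SAE tables are by system organ class and preferred term only, and severity is broken down only for TEAEs.

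**Conclusion.** The point holds as a gap in definition. SAP 8.7.2 assigns events by start date and keeps ongoing pre-dose events out of the TEAEs, and no passage brings them back if they worsen or become serious. Whether a given worsening is lost depends on how the site records it, and the documents do not settle that.

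The size is unknown and probably small. The view that it is small assumes footnote 17 is followed in practice. Any count of affected subjects would rest on assumed rates that the documents do not supply, so none is given. The point deserves attention because the serious, severe and special-interest tables may hold few events, where one case at 1.8 points of an arm can be noticed.

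An unworsened event that leads to stopping drug is a separate matter. It does not belong in a worsening definition and is better handled in the discontinuation table.

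**What to change.** - In Protocol 8.4.1 and 10.2.1 and SAP 8.7.2, define a TEAE as an AE with onset on or after the first double-blind dose, or with earlier onset that increases in severity or becomes serious on or after that dose. Keep the existing end of the window.
- State that such a worsening opens a new AE record or, if the original record is kept, that the date of the change is captured.
- Tabulate AEs leading to discontinuation of double-blind treatment regardless of onset date.
- Reconcile footnote 17 of the Schedule of Activities with Protocol 8.4.1 on which pre-dose AEs are recorded.

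The cost is a few sentences across the two documents, one AE-page completion rule and a change of scope for one table. The downside is that TEAE counts may rise slightly. SAP 8.9 reports the committee's reviews in the past tense, so data collection may be well advanced. If so, pre-dose AEs ongoing at Visit 3 could be reviewed before unblinding to find any that later worsened or became serious.
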